⁴ Griffin KH, Nate KC, Rivard RL, Christianson JB, Dusek JA. Referrals to integrative medicine in a tertiary hospital: findings from electronic health record data and qualitative interviews. BMJ Open. 2016 Jul 25;6(7):e012006. doi: 10.1136/bmjopen-2016-012006.

⁵ Nahin RL, Barnes PM, Stussman BJ. Insurance coverage for complementary health approaches among adult users: United States, 2002 and 2012. NCHS data brief, no 235. Hyattsville, MD: National Center for Health Statistics. 2016.

⁶Fletcher CE, Mitchinson AR, Trumble EL, Hinshaw DB, Dusek JA. Perceptions of other integrative health therapies by Veterans with pain who are receiving massage. J Rehabil Res Dev. 2016;53(1):117-26. doi: 10.1682/JRRD.2015.01.0015.

seem to modulate pain by reducing the level of attention paid to noxious stimuli, thereby suppressing transmission of painful sensations to the cerebral cortex. ^{10,11} When used in addition to usual care (opioid analgesics, with or without non-interactive distraction therapies), VR has been shown to provide clinically and statistically significant reduction in subjective pain score ratings. ^{12,13} The immersive nature of VR makes it a more engaging form of distraction therapy compared to playing a video game or listening to music (e.g. rather than watching a video of a beach, one visually and acoustically experiences being at the beach). Additionally, VR is becoming increasingly portable and affordable with growing availability of thematic content such that patients may select VR experiences that interest them.

Despite growing evidence to the benefit of VR for pain management, no research has yet elucidated its role in outpatients with cancer-related pain.

PURPOSE

The purpose of this research project is to evaluate the impact of virtual reality therapy on mitigating moderate to severe cancer pain in outpatients.

AIMS and HYPOTHESES

Specific Aim 1: To collect and compare pilot data on the impact of a VR intervention against standard care (pre-enrollment analgesic regimen) on pain management measures for outpatients with cancer who have a baseline pain self-rated at least 4/10 (0=no pain, 10=worst pain).

Hypothesis 1: Patients with cancer receiving a virtual reality (VR) intervention will have significantly larger improvements in self-reported pain scores, satisfaction with pain management, lower distress, greater well-being, and lower as-needed opioid use compared to their baseline.

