Because of the nature of the compared interventions, subjects and researchers cannot be blinded to intervention. Our primary outcome measure will determine the impact of VR on self-reported pain score in the last week (numeric rating scale, collected weekly). Self-reported pain experience remains the standard for clinical pain research. Secondary outcomes will measure pain interference (PROMIS Pain Interference Short Form, collected weekly), as-needed opioid use for patients taking opioid analgesics at the time of enrollment (self-reported using medication administration form), satisfaction with VR intervention and overall pain management (collected weekly), and survey of preferences for VR thematic content (collected after Week 4).

Following consent, subjects will complete baseline outcome assessments including self-reported pain score in the last week, the PROMIS Pain Interference Short Form, as-needed opioid use in the last week if applicable, and satisfaction with overall pain management. Subjects will then be provided with a VR headset and paired Touch controllers to bring home for the duration of the study and instructions on the frequency of use for each week. A member of the research will educate the patient on the technology and assure comfort with use. The research study coordinator will contact patients by phone at the end of each week to confirm dates and duration of use as specified by the study protocol, collect self-reported pain score in the last week, the PROMIS Pain Interference Short Form, as-needed opioid use in the last week if applicable, and satisfaction with the VR intervention and overall pain management. Additionally, participants will be surveyed on preferences for VR thematic content at the end of Week 3.

Participants will be monitored for adverse effects and harm for the duration of the study. Although well tolerated in previous studies of patients with cancer and advanced heart failure, potential risks may include dizziness, nausea, eye strain, and loss of confidentiality if data security is breached. Participants are instructed to only utilize the VR device while in a seated or reclined position and to never use the device when standing or ambulating due to the risk of potentially serious injury from falling.

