Descriptive analyses will be performed to summarize baseline characteristics, including initial pain measures from self-report pain rating scale and PROMIS Pain survey. Preferences for VR thematic content and satisfaction with VR intervention will also be summarized. Summary statistics include frequency (%) for categorical variables and mean, standard deviations, median and IQR (1st and 3rd quartile) for continuous variables. Paired t-test or Wilcoxon sign rank test will be used to compare each

time point (end of weeks 1, 2, and 3) to the baseline (beginning of week 1) regarding pain score and PROMIS survey outcomes. Linear mixed-effects model will be used to assess the trend of pain score over the study period controlling for pain medication usage and other covariates (e.g., age, sex).

Data Collection Plan:

Time of Data Collection	Method of Data Collection+	Data Elements Collected
Beginning of Week 1 (Time of Enrollment)	Patient Survey (all patients)	 Self-reported pain score PROMIS Pain Interference Short Form As-needed opioid use* Satisfaction with overall pain management
End of Week 1	Patient Survey (all patients)	 Self-reported pain score PROMIS Pain Interference Short Form As-needed opioid use* Satisfaction with VR intervention and overall pain management
End of Week 2	Patient Survey (all patients)	 Self-reported pain score PROMIS Pain Interference Short Form As-needed opioid use* Satisfaction with VR intervention and overall pain management
End of Week 3	Patient Survey (all patients)	 Self-reported pain score PROMIS Pain Interference Short Form As-needed opioid use* Satisfaction with VR intervention and overall pain management Preferences for VR thematic content

* Data collected for patients receiving as-needed opioid analgesics at the time study enrollment

+ Patient survey administered by Research Coordinator by phone, data entered into Tonic Health

DATA SHARING

Data collected over the course will include summary findings of N = 60 enrolled participants. Per MHRI policy and in full alignment with NIH policy, all data compiled from this and future projects related to data collected in this study will be available upon request by any academic or government researcher, with data shared via existing pathways built to ensure transparency but protect participants. As part of the NIH data sharing directive, de-identified data from this study will be transferred to the PCRC De-Identified Data Repositories.

RECORD RETENTION

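### Hypothesis 1 predicts better satisfaction with pain management and lower as-needed opioid use than at baseline, but neither change has a planned comparison, and the survey items shown do not cleanly support one.

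*Combined protocol and SAP*

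**What the plan says.** Hypothesis 1 (AIMS and HYPOTHESES) predicts "significantly larger improvements in self-reported pain scores, satisfaction with pain management, lower distress, greater well-being, and lower as-needed opioid use compared to their baseline". STUDY DESIGN AND METHODS lists among the secondary outcomes "as-needed opioid use for patients taking opioid analgesics at the time of enrollment" and, collected weekly, satisfaction with both the VR intervention and overall pain management. The Data Collection Plan table schedules as-needed opioid use and satisfaction with overall pain management at baseline and at the end of each of the three weeks.

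DATA ANALYSIS names these analyses:

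- Paired tests: "Paired t-test or Wilcoxon sign rank test will be used to compare each" of the three weekly follow-ups "to the baseline (beginning of week 1) regarding pain score and PROMIS survey outcomes".
- A linear mixed-effects model to "assess the trend of pain score over the study period controlling for pain medication usage and other covariates", such as age and sex.
- Descriptive summaries of baseline characteristics, and: "Preferences for VR thematic content and satisfaction with VR intervention will also be summarized".

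The list of data taken from electronic health records adds average daily oral morphine equivalents (OMEs) for the week before enrollment and for the study period, to be reported as weekly averages.

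**The concern.** The hypothesis and the analysis do not meet. Two outcomes that are hypothesised to change from baseline, named as secondary and scheduled four times, are missing from the only sentence that compares anything with baseline. Medication use appears in the model as something to adjust for, not as something to estimate.

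The Background motivates VR partly by reliance on opioids and by reports of lower opioid use, so an opioid-sparing result is one that readers will look for. With no measure, analysis set or method fixed beforehand, any such statement would rest on choices made after the data are seen, in an uncontrolled, unblinded study. The protocol also says that its results will supply effect size and variance for a larger study, yet it plans no estimate of change for these two outcomes.

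**Working it through.** No stated figure needs reproducing. The check sets the hypothesis, the survey items and the analysis side by side.

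| Outcome | In Hypothesis 1 | Baseline item | Follow-up item | Planned comparison with baseline |
|---|---|---|---|---|
| Pain score | yes | 0-10 average, last week | same | yes |
| Satisfaction with pain management | yes | overall pain management, 0-10 | same scale, but wording includes the headset | none |
| As-needed opioid use | yes | currently taken, yes/no | number of doses, last week | none |
| Distress | yes | none shown | none shown | none |
| Well-being | yes | none shown | none shown | none |
| PROMIS Pain Interference | no | Short Form 6b | same | yes |

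**Count.** Hypothesis 1 names five outcomes. Three are measured, and one of those three (pain) has a planned comparison.

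**Could the existing text already cover the other two?**
- The PROMIS outcomes in the comparison sentence are those of the Pain Interference form. Opioid doses and satisfaction are separate survey questions.
- Adjusting the pain model for medication does not estimate a change in medication.
- Summarising satisfaction with VR is not a comparison with baseline, because VR has not been used at baseline.

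**Could the comparison be run on the surveys as shown?**
- Opioids: a yes/no answer cannot be subtracted from a dose count. STUDY DESIGN AND METHODS plans as-needed use in the last week at baseline and mentions a self-reported medication administration form, but the form's content is not shown. OMEs do have a baseline week, but they measure average daily opioid use, not as-needed doses.
- Satisfaction: a difference between the two items mixes real change with the change in wording.

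**Number of comparisons.** Now: 2 outcomes × 3 time points = 6. With both outcomes added: 4 × 3 = 12. As an illustration only, assuming independent tests at two-sided 0.05 (the plan states neither), the chance of at least one false positive is 1 − 0.95^6 = 0.265 now and 1 − 0.95^12 = 0.460 afterwards. Positive correlation between the tests would lower both.

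**Precision in as-needed opioid users.** The half-width of a 95% interval for a mean change, in SD units of the change, is t(0.975, n−1)/√n. The documents do not give the share taking as-needed opioids; 50-80% is assumed.
- Accrual 60: n = 30 to 48, half-width 0.373 to 0.290 SD.
- Accrual 30, which the protocol accepts: n = 15 to 24, half-width 0.55 to 0.42 SD.

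These are t-intervals for a mean and only indicate the scale. A Hodges-Lehmann interval on skewed dose counts would differ.

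**The case against.** The strongest reply is that less is missing than the comparison sentence suggests. A reader might infer that opioid use is never reported and that satisfaction with pain management has no analysis at all. The documents do not support either reading. OMEs are to be reported as weekly averages, with the pre-enrollment week available, so a description of opioid use over time is planned. In weeks 1 and 2 the only satisfaction item shown is the combined one on overall pain management including the headset, so the planned summary of satisfaction with VR may well be a summary of that item. Both points stand. They narrow the gap to the absence of any planned change from baseline and of any analysis specific to as-needed use.

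A second reply is that this is a single-arm pilot meant to inform a larger study, that the outcomes are secondary, and that further tests double the number of comparisons. That bears on how the results should be presented: as secondary estimates with intervals. It does not remove the mismatch, because Hypothesis 1 is worded as a significant improvement. Labelling both outcomes descriptive and narrowing Hypothesis 1 would also restore consistency, but would give up the opioid question.

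A third reply is that adding a test alone would not work, because the baseline and follow-up items differ. That is correct, and it is why the remedy must start with the survey.

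**Conclusion.** The point holds in this form: two of the three measured Hypothesis 1 outcomes, satisfaction with pain management and as-needed opioid use, have no planned comparison with baseline, and the survey items shown do not support a clean one. This rests on the text and on the surveys as shown. If the medication administration form records a baseline dose count, the opioid data problem disappears, but the missing analysis remains.

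It should be corrected, but it does not threaten the primary pain analysis. The precision figures are secondary to the finding and depend on the assumed 50-80% share. They are noticeably wider at the accepted accrual of 30 than at 60.

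**What to change.** 1. Put the follow-up dose-count question into the baseline survey for participants who take as-needed opioids, or state that the medication administration form supplies the baseline count. Use change in weekly average OME as a supporting measure.
2. Ask the baseline-worded item on satisfaction with overall pain management unchanged at every follow-up, and ask satisfaction with VR as a separate item.
3. Extend the comparison sentence in DATA ANALYSIS to cover, for each week against baseline, as-needed doses (in participants on as-needed opioids at enrollment) and satisfaction with overall pain management. Use the Wilcoxon signed-rank test with the Hodges-Lehmann change and its 95% confidence interval, labelled secondary.
4. Do not reuse the pain mixed model for opioid use with medication usage as a covariate, since opioid use would then be adjusted for itself.
5. Remove distress and well-being from Hypothesis 1, since no survey shown measures them.

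The cost is about a paragraph of analysis text, small survey changes and a few tables. Paired comparisons rise from 6 to 12, so the new results should be presented as secondary estimates with intervals. Precision in opioid users will be limited if accrual is near 30. Anyone enrolled before the survey changes would have a baseline count only if the medication form recorded it.

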- All de-identified data that are collected and entered will remain in the PCRC Data Repositories indefinitely. This de-identified information could be used for future research studies or distributed to other investigators for future research studies without obtaining additional informed consent from you or your legally authorized representative. All future data analysis will be performed on de-identified data in the PCRC Data Repositories. When information and data resulting from this study is presented at scientific meetings or published in a scientific journal, your identity will not be revealed. Quantitative and qualitative data will be presented in aggregate reports and only anonymous excerpts from qualitative data will be used.

Baseline/Time of Enrollment

- 1. In the last week, how would you report your average level of pain with 0 being no pain and 10 being the worst possible pain
- 2. Do you currently take opioid pain medications on an "As Needed" basis as prescribed by your doctor to help manage your pain?
- 3. In the last week, how satisfied have you been with your overall pain management (0 being extremely dissatisfied and 10 being extremely satisfied)
- 4. PROMIS Pain Interference Short Form (see below)

At the end of Weeks 1 and 2

- 1. In the last week, how would you report your average level of pain with 0 being no pain and 10 being the worst possible pain
- 2. If you currently take opioid pain medications on an "As Needed" basis as prescribed by your doctor to help manage your pain, how many doses have you taken in the last week?
- 3. In the last week, how satisfied have you been with your overall pain management, including use of the virtual reality headset (0 being extremely dissatisfied and 10 being extremely satisfied)
- 4. PROMIS Pain Interference Short Form (see below)

At the end of Week 3

- 1. In the last week, how would you report your average level of pain with 0 being no pain and 10 being the worst possible pain
- 2. If you currently take opioid pain medications on an "As Needed" basis as prescribed by your doctor to help manage your pain, how many doses have you taken in the last week?
- 3. In the last week, how satisfied have you been with your overall pain management, including use of the virtual reality headset (0 being extremely dissatisfied and 10 being extremely satisfied)
- 4. PROMIS Pain Interference Short Form (see below)

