- 5. In the last week, how would you report your average level of pain with 0 being no pain and 10 being the worst possible pain
- 6. If you currently take opioid pain medications on an "As Needed" basis as prescribed by your doctor to help manage your pain, how many doses have you taken in the last week?
- 7. In the last week, how satisfied have you been with your overall pain management, including use of the virtual reality headset (0 being extremely dissatisfied and 10 being extremely satisfied)
- 8. PROMIS Pain Interference Short Form (see below)
- 9. Did you find the VR program easy to use (yes/no)?
- 10. How much did you enjoy the VR program (0 being not at all and 10 being very much)?
- 11. While you were using the VR headset, how immersed did you feel in the virtual environment. Alternatively, to what extent did you feel like you "went into" the virtual environment (0 being not at all and 10 being very much)?

- 12. Do you prefer a virtual environment in which you are mostly observing the world around you, or in which you can participate, move around, or engage in activities (active or passive)?
- 13. Do you prefer a virtual environment that is realistic, such as a video of a real location, or simulated, such as computer-generated graphics (realistic or simulated)?

Data collected from electronic health records:

- 1. Participant demographics
 - a. Age
 - b. Sex
 - c. Race
 - d. Ethnicity
- 2. Medical history
 - a. Cancer type
 - b. Time since diagnosis
 - c. Analgesic use (on opioids at baseline (Y/N); if yes, if taking short-acting, longacting, or both; average daily oral morphine equivalents used at the time of enrollment (accounting for the week prior to enrollment) and for the duration of the study period. Daily OMEs will be reported as weekly averages.

PROMIS Item Bank v1.0 - Pain Interference - Short Form 6b

Pain Interference – Short Form 6b

Please respond to each item by marking one box per row.

In the past 7 days...

	-	Not at all	A little bit	Somewhat	Quite a bit	Very much
PAININ3	How much did pain interfere with your enjoyment of life?		2		4	5
PAININ8	How much did pain interfere with your ability to concentrate?		2	3	4	5
PAININ9	How much did pain interfere with your day to day activities?		2	3		5
PAININ10	How much did pain interfere with your enjoyment of recreational activities?		2	3	4	5
PAININ14	How much did pain interfere with doing your tasks away from home (e.g., getting groceries, running errands)?		2 2		4	5

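### The printed baseline survey asks only yes/no about as-needed opioids and takes no dose count, so it supports none of the three possible changes from baseline

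*Combined protocol and SAP*

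**What the plan says.** Hypothesis 1 (AIMS and HYPOTHESES) sets as-needed opioid use against the participant's own baseline. STUDY DESIGN AND METHODS makes it a secondary outcome: "as-needed opioid use for patients taking opioid analgesics at the time of enrollment (self-reported using medication administration form"). The same section lists, among the baseline assessments, "as-needed opioid use in the last week if applicable, and satisfaction with overall pain management".

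The Data Collection Plan table under DATA ANALYSIS has as-needed opioid use in all four rows, from the beginning of Week 1 to the end of Week 3. The method in each row is "Patient Survey (all patients"). Its footnote reads "Data collected for patients receiving as-needed opioid analgesics at the time study enrollment".

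The survey instruments differ by time point. Baseline item 2 begins "Do you currently take opioid pain medications on an" as-needed basis and can be answered yes or no. From the end of Week 1, item 2 begins "If you currently take opioid pain medications on an" as-needed basis and ends "how many doses have you taken in the last week". The Week 3 list prints this weekly item twice, as items 2 and 6.

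Separately, the list of health-record data includes "average daily oral morphine equivalents used at the time of enrollment (accounting for the week prior to enrollment") and over the study period, reported as weekly averages, with a note of whether the opioid is short-acting, long-acting or both.

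**The concern.** The text promises a baseline quantity that the printed instrument does not collect. In this design the baseline carries the whole comparison. The study is non-randomized, every participant receives VR, and Aim 1 defines standard care as the regimen before enrollment. The first dose count covers Week 1, when participants are already using VR daily, so it cannot stand in for a pre-VR value.

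The pilot is also meant to supply effect size and variance for planning a larger study. For as-needed opioid use, a survey without a baseline count gives neither the mean change nor its variance. If nobody asks for the last-week count at enrollment, it can be recovered only by later recall or from a form whose content is not described.

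**Working it through.** No plan figure needs reproducing and no formula is in dispute. The check is what each source records at each time point.

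| Time point | Data Collection Plan lists as-needed use by survey | Dose count in the printed survey |
|---|---|---|
| Beginning of Week 1 | yes | none (item 2 is yes/no) |
| End of Week 1 | yes | yes (item 2) |
| End of Week 2 | yes | yes (item 2) |
| End of Week 3 | yes | yes (items 2 and 6, the same question) |

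1. Let D0 be as-needed doses in the week before enrollment and D1, D2, D3 the counts for the three study weeks. Change from baseline in week k is Dk − D0.
2. The survey gives D1, D2 and D3 but not D0. Dose counts are available at 3 of 4 time points.
3. All three differences, D1 − D0, D2 − D0 and D3 − D0, need D0. The number that can be formed from the survey is 0 of 3, for every participant.
4. What remains is a coarse contrast: user yes/no at enrollment against some or no doses later. It shows whether a baseline user reports no doses in a later week, not whether someone took fewer.
5. Other sources:
   - *Medication administration form.* It appears once, in the secondary-outcome sentence. Its content and timing are not given, and the Data Collection Plan names only the survey. It may or may not hold D0.
   - *Health-record morphine equivalents.* These cover the week before enrollment and the study weeks, so a change can be formed. They are not described as specific to as-needed doses. The short-acting/long-acting classification helps to describe regimens, but short-acting does not mean as-needed.

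Two wording points sit beside this; neither blocks a change score. First, the weekly count is put to those currently taking as-needed opioids, whereas the footnote fixes the group at enrollment. Second, the secondary-outcome sentence speaks of patients on opioid analgesics at enrollment, and the footnote of patients on as-needed opioids at enrollment. A participant on long-acting opioid alone falls under the first description and not the second.

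**The case against.** The best defence is that the survey is not the only named source. The outcome sentence points to the medication administration form, and a form that has not been shown cannot be presumed to lack a baseline count. The health record also supplies an opioid measure with a baseline. This stands as a limit on scope: a reader might infer that the trial cannot measure change in opioid use at all, and the documents do not support that. It does not remove the mismatch, because the Data Collection Plan assigns the baseline item to the survey and the survey does not carry it.

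A reader might also infer that the weekly wording will drop participants who stop as-needed opioids and so hide a reduction. Taken literally the item could skip them, but the footnote already ties collection to as-needed users at enrollment, a coordinator administers the survey by phone, and someone who still has the prescription but took none can answer 0. This is a wording risk. The documents give no stopping rates and no dose distribution, so any bias figure would rest wholly on assumed inputs. Such a figure for the survey's change score would also presuppose the baseline count that the survey lacks.

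The population mismatch is mostly editorial: a participant on long-acting opioid alone has no as-needed doses to report, and the methods text says the item is collected if applicable.

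Finally, this is one secondary outcome in a pilot. DATA ANALYSIS names paired tests only for pain score and PROMIS, and the sample-size text does not say that the larger study will be sized on opioid use. That limits the importance of the point. It does not answer it, since Hypothesis 1 names the comparison and even a descriptive change needs a baseline value.

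**Conclusion.** The point holds for the printed survey. Hypothesis 1 needs as-needed opioid use at baseline, the methods text and the Data Collection Plan say it is collected, and the baseline survey takes only a yes or no. Its size is 0 of 3 changes from baseline computable from the survey. The missing baseline count alone causes this; the weekly wording and the population wording do not contribute.

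The conclusion assumes that the survey is administered as printed. For the trial as a whole it is conditional: if the medication administration form records last-week as-needed doses at enrollment, the data exist and the fault is one of documentation. Change in total opioid use can still be examined through morphine equivalents. The primary pain-score outcome is not affected, and no direction or amount of bias is claimed.

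The sponsor should correct this, because a named secondary outcome is affected and the remedy is small.

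**What to change.** Add to the baseline survey, for participants who answer yes to item 2, a question on the number of as-needed opioid doses taken in the last week, with the same recall period and unit as the weekly item. Keep the yes/no item to define the group. If the medication administration form is the intended source, say so in the Data Collection Plan and require it to record this count at enrollment.

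As a secondary wording correction, ask the weekly dose count of every participant who was an as-needed user at enrollment, and record the actual number, including 0. Make the same change to the Week 3 duplicate (item 6) or delete it. Align the population in the secondary-outcome sentence with the footnote.

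The cost is one extra baseline entry for as-needed users and a few edits to survey and protocol text. Participants are already surveyed at all four time points, so no extra contact is needed.

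### The enrollment survey asks whether as-needed opioids are taken but not how many doses, so unless a form not shown holds that count, the hypothesised change from baseline in as-needed use cannot be computed

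*Combined protocol and SAP*

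**What the plan says.** **What is to be compared.** Under AIMS and HYPOTHESES, Hypothesis 1 predicts "lower as-needed opioid use compared to their baseline". STUDY DESIGN AND METHODS makes as-needed opioid use a secondary outcome among patients on opioids at enrollment, and gives its source as "self-reported using medication administration form".

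**What is to be collected.** The same section lists, among the baseline assessments, "as-needed opioid use in the last week if applicable, and satisfaction with overall pain management". The Data Collection Plan table puts as-needed opioid use at enrollment and at the end of Weeks 1, 2 and 3, with a patient survey as the method each time. Its footnotes read "Data collected for patients receiving as-needed opioid analgesics at the time study enrollment" and "Patient survey administered by Research Coordinator by phone, data entered into Tonic Health".

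**What the surveys ask.** Enrollment item 2 begins "Do you currently take opioid pain medications on an" as-needed basis. It asks for no number and sets no recall period. The Week 1, 2 and 3 item begins "If you currently take opioid pain medications on an" as-needed basis and goes on to ask "how many doses have you taken in the last week".

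**What is to be analysed.** DATA ANALYSIS applies the paired t-test or Wilcoxon comparison with baseline to the pain score and PROMIS pain interference. Pain medication appears there only as an adjustment variable in the mixed model for pain score. Separately, the list of health-record items includes mean daily morphine-equivalent dose (OME) for the week before enrollment and during the study, summarised by week. No analysis is attached to it.

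**The concern.** The study has one arm, and each participant's own baseline is the comparator. No control group can stand in for a baseline value that was not collected. A yes/no answer cannot be subtracted from a weekly count, so the survey as written does not give the change that Hypothesis 1 is about. It would support only comparisons among Weeks 1, 2 and 3, all of them after VR has started.

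The pilot is also meant to supply effect size and variability for planning a larger study. For as-needed opioid use, neither the change from baseline nor its variance could be estimated from the survey.

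A second effect is possible. The mixed model for pain score adjusts for medication use without saying which measure is meant. If it is the survey dose count, that covariate has no value at enrollment.

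**Working it through.** The plan gives no figure to reproduce on this point. The check sets the plan's requirement beside the instrument shown.

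| Time point | As-needed use required by the table? | Survey item shown | Dose count obtained? |
|---|---|---|---|
| Enrollment | Yes | Whether as-needed opioids are taken | No |
| End of Week 1 | Yes | Number of doses in the last week | Yes |
| End of Week 2 | Yes | Number of doses in the last week | Yes |
| End of Week 3 | Yes | Number of doses in the last week | Yes |

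1. **Counts available.** 3 of 4 time points.
2. **Contrasts with baseline.** The change at week w is (doses at week w) minus (doses at enrollment), for w = 1, 2, 3. The second term is absent in all three, so 0 of 3 can be computed from the survey.
3. **Planned paired comparisons.** 2 outcomes (pain score, PROMIS) × 3 weeks = 6. None concerns opioid use.
4. **Other possible sources of a baseline.**
   - *Medication administration form.* It is named once, in STUDY DESIGN AND METHODS. It is not reproduced, and neither the DATA COLLECTION text nor the Data Collection Plan table mentions it. Whether it holds a count for the week before enrollment cannot be checked.
   - *Health-record OME.* This does cover the week before enrollment and the study weeks. It applies to patients on short-acting opioids, long-acting opioids or both, and no split into as-needed and scheduled use is stated. It therefore gives a change in total opioid use, not in as-needed use.
5. **Follow-up wording.** Because the Week 1-3 item is conditional on current use, a baseline user who has stopped could be left blank rather than scored 0. That would remove exactly the patients with the reduction that the hypothesis predicts.
6. **Mixed model.** If the medication covariate is OME, it has an enrollment value. If it is the weekly survey count, it does not. The plan does not say which is meant.

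**The case against.** The strongest reply is that the protocol body states the requirement correctly: last-week as-needed use is listed at baseline, and a dedicated form is named for the outcome. On this view, one survey item falls short of the requirement, which is not the same as the count going uncollected. That stands, and it is why the consequence is conditional. It does not remove the mismatch, because the Data Collection Plan names the patient survey as the method at all four time points.

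The item may also be a drafting slip rather than a choice. The Week 3 survey repeats its first four questions as items 5 to 8, which suggests incomplete editing. This bears on the cause, not on the need to correct it.

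A reader might infer three stronger things that the documents do not support:

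- *That no baseline opioid quantity exists, or that any first-week change in opioid use is lost.* Weekly OME gives a baseline-to-Week-1 contrast in total use, and the form may give one in as-needed use.
- *That the primary pain outcome is untouched.* The paired pain-score comparisons do not use opioid data, but the mixed model adjusts for an undefined medication measure, so this cannot be asserted for the model.
- *That the primary analysis is compromised.* This does not follow either, since the covariate may be OME.

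Finally, in a pilot, the absence of a named test for opioid use would by itself be only missing detail. That is fair. The point rests on the missing baseline count.

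**Conclusion.** The point holds in a limited form. The enrollment item does not deliver what Hypothesis 1, the methods text and the data collection table require, and from the surveys shown 0 of 3 baseline contrasts in as-needed doses can be formed. Confidence in this mismatch is high, because it is read directly from the text.

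The consequence is that change from baseline in as-needed use cannot be computed. This rests on the assumption that the medication administration form holds no baseline count, so confidence here is moderate. What is affected is one secondary outcome, in the subgroup taking as-needed opioids at enrollment. The documents do not give the size of that subgroup. Total opioid use keeps a baseline through OME but has no assigned analysis. An effect on the pain-score mixed model arises only if the survey count is its medication covariate.

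**What to change.** 1. Add the Week 1-3 dose question to the enrollment survey, with the same one-week recall. If the medication administration form already records that count, say so and name it as the source.
2. At follow-up, record 0 for any baseline as-needed user who took no doses.
3. Report change from baseline at Weeks 1, 2 and 3 with confidence intervals, among as-needed users at enrollment, using the paired t-test or Wilcoxon approach already planned.
4. Report weekly-average OME alongside as a supporting measure, so that a lower count that goes with a regimen change can be recognised. State that it is not split into as-needed and scheduled use, and that health-record values may reflect prescribed rather than taken doses.
5. Say which measure is the medication covariate in the mixed model.
6. For anyone enrolled before the change, take the baseline count from the form if it is there. Otherwise report that the change in as-needed use is not available.

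The cost is one question at enrollment, a recording rule and a few sentences in DATA ANALYSIS. The downsides are some recall error and three more comparisons in a pilot (6 + 3 = 9), which is why estimates with intervals should carry the reporting. In return, 3 of 3 baseline contrasts become computable for participants asked the new question.
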